5. STUDY PROCEDURES

The sections that follow provide an overview of the procedures that are to be followed in enrolling, evaluating, and following subjects who participate in this clinical study. Visits can be either clinic visits or safety follow-up telephone calls, as specified in the Table below and in the [Time and Events Table 2, 3 and 4](#).

Table 5-1: Study Procedures

Visit Category	Procedures
Vaccination Clinic Visit – Pre-vaccination Procedures	Section 5.1. describes procedures to be followed prior to study vaccination: informed consent, screening, enrolment, and randomization
Vaccination Clinic Visit(s) – Vaccination and Post-vaccination Procedures	Section 5.2 describes procedures to be followed during each clinic visit involving vaccination: vaccination, post-vaccination procedures, and post-vaccination reminder calls
Post-vaccination Visit(s)	Section 5.3 describes follow-up clinic visits, safety follow-up calls, and active ILI surveillance calls
Unscheduled Visit(s)	Section 5.4 describes possible procedures to be followed at unscheduled clinic visits
Study Termination Visit	Section 5.5 describes procedures to be followed at the last study visit for a subject (may include early termination visit)

5.1 Vaccination Clinic Visit - Pre-vaccination Procedures

This section describes the procedures that must be performed for each potential subject prior to vaccination, including obtaining informed consent, screening, enrolment and randomization. Please refer to [Time and Events Table 2](#).

5.1.1 Informed Consent

"Informed consent" is the voluntary agreement of an individual or his/her legal guardian(s) to participate in research. Consent must be given with free will of choice, and without undue inducement. The individual must have sufficient knowledge and understanding of the nature of the proposed research, the anticipated risks and potential benefits, and the requirements of the research to be able to make an informed decision.

Informed consent following local IRB/EC guidance **must** be obtained before conducting any study-specific procedure (i.e., all of the procedures described in the protocol). The process of obtaining informed consent should be documented in the subject source document in addition to maintaining a copy of the signed and dated informed consent.

If a subject or legal guardian is unable to read, an impartial witness should be present during the entire informed consent discussion. An impartial witness is defined as a person who is independent from study conduct, who cannot be unfairly influenced by those involved with the study, who attends the informed consent process if the subject or, if applicable, the subject's legally acceptable representative cannot read, and who reads the informed consent form (ICF) and any other written information supplied to the subject. After the written ICF and any other written information to be provided to subjects, is read and explained to the subject or legal guardian and after the subject or legal guardian has verbally consented to the subject's participation in the study and, if capable of doing so, has signed and personally dated the ICF, the witness should sign and personally date the consent form. By signing the consent form, the witness attests that the information in the consent form and any other written information was accurately explained to, and apparently understood by, the subject or legal guardian and that informed consent was freely given by the subject or legal guardian.

The informed consent process may be conducted within 10 days prior to Day 1.

5.1.2 Screening

After an individual has consented to participate in the study and informed consent is signed, that individual will be given a unique Screening Number. The subject's unique Screening Number will be documented in the Screening and Enrolment log. The eligibility of the subject will be determined based on the inclusion and exclusion criteria listed in [Section 4, Selection of Study Population](#) and evaluated during this screening procedure.

Prior to study enrolment, demographic data will be collected from the subject, including: age, sex, race, ethnicity, height and weight, prior influenza vaccination, smoking status and, comorbidity and risk of complications from influenza indicated by a calculated score. The risk assessment which incorporates medical comorbidity among other baseline characteristics is a validated predictor of risk of complications from influenza in subjects ≥ 65 years of age ([Hak, 2004](#)) (see [Table 5.1.2-1, Prediction Rule for Estimating the Probability of Hospitalization Due to Pneumonia or Influenza and Death Due to Any Cause](#)). Using this model, a score of <50 is considered low risk and a score of ≥ 50 is considered high risk.

It is important to note that the determination of pre-existing medical conditions, for the purpose of calculating the risk score, should be made by the investigator based on his or her clinical judgment. A list of conditions which are associated with increased risk of complications from influenza are presented in [Appendix 1](#) as a reference for the Investigator (Website CDC and [Mullooly et al., 2007](#)).

Table 5.1.2-1: Prediction Rule for Estimating the Probability of Hospitalization Due to Pneumonia or Influenza and Death Due to Any Cause (Hak, 2004)

Characteristic	Score ^a
Age, years	
<70	0
70-74	14
75-79	28
80-89	42
≥90	56
Sex	
Female	0
Male	9
Outpatient visits during the previous year	
0	0
1-6	11
7-12	22
>13	33
Previous hospitalization due to pneumonia or influenza	
No	0
Yes	63
Comorbidity^b	
Pulmonary disease	18
Heart disease	6
Renal disease or renal transplant	12
Dementia or stroke	22
Non-hematological and hematological cancer	48
Notes:	
^a The prognostic score for a given subject can be obtained by adding the scores for each applicable characteristic.	
^b Pre-existing medical conditions of eligible subjects will be scored following judgment by the investigator. Appendix 1 provides a list of conditions with examples to provide guidance to the investigator.	

Medical history will also be collected, including but not limited to any medical history that may be relevant to subject eligibility for study participation such as prior vaccinations, concomitant medications, and previous and ongoing illnesses or injuries. Relevant medical history should also include any medical history that contributes to the

understanding of the risk score and of an adverse event that occurs during study participation, if it represents an exacerbation of an underlying disease/pre-existing problem.

Review of systems is a structured interview that queries the subject or legal guardian as to any complaints the subject has experienced across each organ system. This will be performed before enrolment and used to guide physical examination.

If applicable, prior and concomitant medications or vaccinations taken prior to start of study should be collected (refer to [Section 6.5, Prior and Concomitant Medications and Vaccines](#) for further details).

Collection of vital signs is to be performed: heart rate, blood pressure, respiratory rate and pre-vaccination body temperature (preferably oral). If body temperature is $\geq 38.0^{\circ}\text{C}$ (or $\geq 100.4^{\circ}\text{F}$) at the time of screening, vaccination must be postponed until 3 days after the fever has resolved (see [Section 4.3, Criteria for Delay of Vaccination](#)).

Measure height and weight. Measurement and recording of vital signs, height, weight and body temperature, may be conducted by a trained health care professional.

A general physical examination is to be performed by a qualified health care practitioner. “Qualified health care practitioner” refers to any licensed health care professional who is permitted by institutional policy to perform physical examinations and who is identified within the Study Staff Signature Log.

The data described above will be written in the source document (see [Section 9.1, Source Documentation](#)). Should the physical assessment reveal any abnormal values or events, these must be documented as part of medical history.

Prior to vaccination, approximately 10 mL of blood will be drawn from approximately 2800 subjects participating in the immunogenicity season (see [Section 3.5, Collection of Clinical Specimens](#)).

In the event that the individual is determined ineligible for study participation, he/she is considered a screen failure. The reason for screen failure must be documented in the Screening and Enrolment log. If the individual is determined to be eligible for the study, he/she will be enroled into the study.

5.1.3 Enrollment

After signing the ICF, if an individual is determined to be eligible for study participation, the investigator or delegate will enroll the subject and enter subject information and stratification information into the Interactive Response Technology (IRT) system.

5.1.4 Randomization

Enroled subjects will be randomized in the IRT system by a 1:1 ratio to receive either aQIV or the non-influenza comparator vaccine Boostrix® and will be automatically assigned a unique Subject ID and Pack ID indicating the assigned treatment. The Subject ID will be the subject's unique identification number for all CRFs and associated study documentation that will be used for duration of the study. The Subject ID consists of a 7-digit number resulting from the combination of the site number, and the subject's order of randomization at the site. After randomization, the Screening Number ceases to be used and remains in the Screening and Enrolment Log only. The list of randomization assignments is produced by the IRT service provider and approved by Seqirus or delegate.

Randomization will be stratified by age (cohorts 65 to 74 years and 75 years and above), study site and also based on risk for complications from influenza (assessment score < 50 or ≥ 50).

If for any reason, after signing the ICF, the subject who is eligible and enroled fails to be randomized, this is called a randomization failure. Further guidance is provided in the CRF Instructions. The reason for all randomization failures should be recorded in the Screening and Enrolment Log and in the source document as specified in the Source Data Agreement (SDA). The information on subjects who are randomization failures should be kept distinct from subjects who are screen failures, as described in [Section 5.1.2, Screening](#).

If for any reason, after randomization the subject fails to undergo treatment, this is an Early Termination and the reason should be recorded in source document as specified in the SDA. The information on these Early Termination subjects should be kept distinct in the source documentation from randomization failures.

Subjects from a single season will have blood samples collected for inclusion in an immunogenicity subset. Samples from approximately 2800 subjects participating in the selected season will be collected at Day 1 (baseline) and Day 22 (visit 3). In order to maintain the study blind equal numbers of subjects from both treatment groups will be asked to provide blood specimens (see [Section 3.5, Collection of Clinical Specimens](#)). The IRT-system will be used to identify subjects from which blood specimens are to be collected. After all of the blood specimens have been collected a randomly selected subset of these samples will be analyzed. Detailed information regarding the randomization procedures associated with the selection of the samples to be analyzed can be found in the Statistical Analysis Plan (SAP).

A subset of approximately 2,100 subjects from multiple seasons and countries participating in the trial will be randomly selected for participation in the solicited safety subset. Equal numbers of subjects from both treatment arms will be selected for participation in this subset. Detailed information regarding the randomization procedures associated with the selection of the subjects participating in this subset can be found in the Statistical Analysis Plan (SAP).

5.2 Vaccination Clinic Visit – Vaccination and Post-vaccination procedures

Please refer to [Time and Events Table 2](#). Vaccination will be performed on Day 1 using the vaccine identified by the assigned Pack ID.

The Day 1 serology sample collected from selected subjects participating in the immunogenicity season must be taken **prior** to vaccination.

After completing the pre-vaccination procedures as described in [Section 5.1, Vaccination Clinic Visit - Pre-vaccination Procedures](#), the vaccine will be administered to the subject according to the procedures described in [Section 6.3, Vaccine Preparation and Administration](#), observing the blinding procedures described in [Section 3.3, Blinding Procedures](#).

Prior to administration of the study vaccination, it needs to be confirmed that the subject is eligible for vaccination and does not meet any criteria for exclusion or delaying study vaccination as described in [Section 4, Selection of Study Population](#).

5.2.1 Post-vaccination Procedures

The following post-vaccination procedures will be performed on Day 1.

Observation Period

After vaccination, the subject will be observed for at least 30 minutes for unsolicited adverse events, solicited adverse events, and a body temperature measurement (preferably oral) will be taken. During this observation period, the subject should be trained on how to use the thermometer and for subjects participating in the solicited safety subset, the ruler provided and how to measure local solicited adverse events (see [Section 7.1.1, Solicited Adverse Events](#)). All safety data collected during this time should be recorded in the subject's source document.

Subject Diary Training

A Subject Diary will be dispensed to subjects participating in the solicited safety subset to document solicited adverse events from Day 1 to Day 7. The Subject Diary is the only

source for collection of these data; therefore, it is critical that the subject completes the Subject Diary correctly. The subject should be trained on how and when to complete each field of the Subject Diary. The Subject Diary should be completed on a daily basis and the entries should be written clearly in pen. See additional rules in [Section 3.4.2, Tools Used for Data Collection](#).

The subject or legal guardian should be trained on how to self-measure local solicited adverse events and body temperature (preferably oral). The measurement of solicited local adverse events is to be performed using the ruler provided by the site.

The subject or legal guardian should be instructed how to perform body temperature measurement using the thermometer provided by the site. If the subject feels unusually hot or cold during the day, the subject or legal guardian should check body temperature. If the subject has fever, the highest body temperature observed that day should be recorded in the Subject Diary.

Subject Diary completion starts on the day of vaccination. The subject will be instructed to check for solicited adverse events approximately 6 hours after the vaccination or prior to going to bed. Entries on subsequent days should be performed around the same time, preferably in the evening.

Subject Diary training should be directed at the individual(s) who will perform the measurements of adverse events and who will enter the information into the Subject Diary. In some situations, the Subject Diary may be completed by somebody other than the subject or legal guardian (except study site personnel). If a person other than the subject or legal guardian enters information into the Subject Diary, the reason that the subject cannot complete their own Subject Diary and the person's identity and relationship to the subject must be documented in the Subject Diary. Any individual that makes entries into the Subject Diary must receive training on completion of the Subject Diary at the time of the visit. This training must be documented in the subject's source record.

The same individual should complete the Subject Diary throughout the course of the study.

Plan Next Study Activities

The site should schedule the next study activity with the subject or legal guardian. It is recommended for the site to already schedule in advance the remaining upcoming study activities.

Discharge

The subject or legal guardian should be reminded to contact the site if there are any questions, and to contact the site immediately (or as soon as the subject is medically stable) if the subject has a medical condition that leads to a hospitalization or an emergency room visit or to a visit to/by a doctor or is otherwise of concern.

An ILI instruction sheet will be provided with instructions for reporting possible ILIs. The subject or legal guardian will be reminded to contact the site immediately if the subject experiences symptoms meeting primary protocol-defined ILI criteria in order to have a NP swab collected for evaluation of the presence of influenza virus. If anti-viral medications (e.g. neuraminidase inhibitors) are prescribed it is recommended that an NP swab be obtained prior to the first dose.

An ILI booklet will be dispensed to document, in case of a protocol-defined ILI, the subject's daily body temperature. The subject or legal guardian will be instructed to start recording the subject's daily body temperature (preferably oral) daily from protocol-defined ILI onset day until the day the subject comes in to the clinic for their NP sample collection. Subjects will be asked to return the ILI booklet at the time of their ILI clinic visit. At the ILI visit the subject's will be given a new ILI booklet in case they experience another ILI.

Completion instructions should be directed at the individual(s) who will enter the information into the ILI booklet. In some situations, the ILI booklet may be completed by somebody other than the subject or legal guardian, except study site personnel. If a person other than the subject or legal guardian enters information into the ILI booklet, the reason that the subject cannot complete the ILI booklet and the person's identity and relationship to the subject must be documented in the ILI booklet. Any individual that makes entries into the ILI booklet must receive completion instructions at the time of the clinic visit. In some countries based on local requirements and practices subjects may also be given a subject identification card which will contain emergency contact information.

5.2.2 Post-vaccination Reminder Calls

Subject Diary Reminder Calls

Subjects participating in the solicited safety subset will receive a diary reminder call on Day 3. The purpose of this call is to remind the subject or legal guardian about completion of the Subject Diary. The call follows the Subject Diary Reminder Phone Call Script provided to the site. The subject or legal guardian should be reminded to contact the site via the telephone number provided in the informed consent to discuss medical questions.

The reminder call is not intended to be an interview for collection of safety data. If the subject or legal guardian wishes to describe safety-relevant information, the call should be continued by a healthcare professional from the study site, and the safety data should be recorded in the subject's medical chart.

5.3 Post-vaccination Visit(s)

Please refer to [Time and Events Table 2](#) and [3](#). Post-vaccination visits will be performed on Days 15, 22, 91, 181, 271 and 366. In the event that a scheduled or unscheduled visit or call/message coincides, procedures may be combined.

5.3.1 Follow-up Clinic Visit(s)

Safety follow-up clinic visits will be performed on Days 22 and 181.

During the follow-up clinic visit on Day 22, for subjects participating in the solicited safety subset, the Subject Diary will be reviewed and collected. No changes to the information recorded within the Subject Diary are permissible. For details on the Subject Diary see [Sections 3.4.2, Tools Used for Data Collection](#) and [5.2.1, Post-vaccination Procedures](#). The subject or legal guardian will be interviewed to determine if any unsolicited adverse events (including SAEs, ILIs, NOCDs, AEs leading to withdrawal and AESIs) occurred and if any concomitant medications or vaccines were taken/received during the time since the last clinic visit. This interview will follow a script which will facilitate the collection of relevant safety information. The healthcare professional reviewing these data will discuss the symptoms (if any) reported by the subject and will determine if any additional diagnoses and/or adverse events are present. All adverse events reported by the subject or legal guardian at this follow-up clinic visit must be recorded in the subject's source document and on an Adverse Events CRF, as specified in [Section 7.1, Safety Assessment](#), and not written on the script used for the interview.

During the follow-up clinic visit on Day 181, the subject will be interviewed to obtain information relating to a subset of unsolicited AEs (all SAEs, ILIs, NOCDs, AEs leading to withdrawal and AESIs) and use of medication to treat these.

During both follow-up clinic visits, the subject will be asked as to whether he or she was hospitalized or was evaluated at an emergency room or a physician's office for any illness since the site's last contact with the subject. If an SAE has been identified by the site staff during the interview which has not previously been reported by the subject, this SAE will be reported by the site within 24 hours to Seqirus or delegate. Any additional relevant medical history will be recorded as needed.

During both follow-up clinic visits, an ILI assessment will be performed to determine if symptoms of ILI are present. Potential ILI symptoms will be documented in the subject's source records. If the onset of the ILI is 6 days or less before the visit, a NP swab should be collected from the subject for influenza testing and study staff will document the ILI on an Adverse Event and ILI CRF (see procedures described in [Section 5.4, Unscheduled Visits](#)).

During both follow-up clinic visits, a brief symptom-directed physical examination will be performed by a qualified health care practitioner according to symptoms the subject has reported. This physical examination will include an examination of organ systems that are considered relevant by the investigator based on review of the subject's reported adverse events, and concomitant medication use. This assessment may include measurement of vital signs (respiratory rate, blood pressure and heart rate), body temperature (preferably oral) and a check of general appearance. The physical assessment must be performed by the investigator or designee of the investigator, who is qualified to perform a physical assessment in accordance with their institutional policy. Measurement and recording of vital signs and body temperature may be conducted by a trained health care professional. Corresponding information is documented in the subject's source document and eCRF(s).

During the Day 22 follow-up clinic visit, approximately 10 ml of blood will be drawn from selected subjects participating in the immunogenicity season (see [Section 3.5, Collection of Clinical Specimens](#)).

The site should also schedule the next study activity, the safety call, with the subject or legal guardian. It is recommended for the site to also schedule in the remaining upcoming study activities whenever possible.

The subject or legal guardian will receive a written reminder of the next planned study activity. The subject or legal guardian will be reminded to contact the site immediately (or as soon as the subject is medically stable) if the subject has a medical condition that leads to a hospitalization, an emergency room visit, or a visit to/by a doctor, or is otherwise of concern.

The subject or legal guardian will be reminded to contact the site immediately if the subject experiences symptoms meeting primary protocol-defined ILI criteria in order to have a NP swab collected for evaluation of the presence of influenza virus. If anti-viral medications (e.g. neuraminidase inhibitors) are prescribed it is recommended that an NP swab be obtained prior to the first dose.

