5.3.2 Safety Follow-up Calls

Safety follow-up calls will be performed on Days 15, 91 and 271.

Safety follow-up calls are calls made to the subject by a healthcare professional designated on the site log. These calls will follow a script which will facilitate the collection of relevant safety information. The subject or legal guardian will be interviewed according to the script. On Day 15, information will be collected regarding all unsolicited adverse events and concomitant medications or vaccinations associated with those events. Safety follow-up calls performed on Days 91 and 271 will collect information relating to a subset of unsolicited adverse events including SAEs, adverse events of special interest (AESIs), AEs leading to withdrawal, new onset of chronic disease (NOCD), ILI and concomitant medications or vaccinations associated with those events. All safety information described by the subject must be written down in a designated location within the source document and not written on the script used for the telephone call.

The subject will be asked as to whether he or she was hospitalized or was evaluated at an emergency room for any illness since the site's last contact with the subject. If an SAE has been identified by the site staff during the interview which has not previously been reported by the subject, this SAE will be reported by the site within 24 hours to Seqirus or delegate. Any additional relevant medical history will be reported to Seqirus or delegate and recorded as needed.

ILI assessments will be performed to determine if symptoms of ILI are present. If the subject reports during phone contact that a medical event has occurred with symptoms consistent with an ILI, the subject will be asked to visit the site for further evaluation and potential NP swab taking. An NP swab should be collected, for evaluation of the presence of influenza virus, preferably within 3, but up to 6, days after the first day of onset of ILI symptoms. See procedures described in [Section 5.4, Unscheduled Visits](#).

The subject or legal guardian will receive a reminder of the next planned study activity. The subject or legal guardian will be reminded to contact the site immediately (or as soon as the subject is medically stable) if the subject has a medical condition that leads to a hospitalization or an emergency room visit or to a visit to/by a doctor or is otherwise of concern.

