5.5 Study Termination Visit

The study termination visit will occur on Day 366. The termination visit must be a clinic visit; unless the subject is early terminated in which case a study termination visit may be a telephone call. The date of termination is the date of the last contact (clinic visit or telephone call) in which the subject's health status was assessed or, in cases where the subject does not agree to any further safety follow-up; it is the date consent is withdrawn. This date should be recorded on the termination eCRF page. For visit procedures to be performed for a subject whose planned study participation ends prematurely, please see [Section 5.5.1, Early Termination Visit](#).

At the clinic visit, the following procedures will be performed:

- Interview the subject to obtain information regarding potential SAEs, ILIs, NOCDs, AEs leading to withdrawal and AESIs and the medication to treat these.
- Ask the subject as to whether he or she was hospitalized or was evaluated at an emergency room for any illness since the site's last contact with the subject. If an SAE has been identified by the site staff during the interview and has not previously been reported by the subject, this SAE must be reported by the site within 24 hours to Seqirus or delegate. Record any additional relevant medical history as needed.

An assessment will be performed to determine if symptoms of ILI are present. Potential ILI symptoms will be documented in the subject's source records. If the onset of the ILI is 3, or at most 6, days before the visit, an NP swab should be

collected from the subject for influenza testing and study staff will document the ILI on an Adverse Event and ILI CRF. See procedures described in [Section 5.4](#),

Unscheduled Visits. Should an ILI be identified, it is recommended to postpone the study termination visit, to allow for the ILI follow-up visit to occur.

- Should the subject have experienced a protocol defined ILI for which an NP swab was obtained, please ensure collection and review of the ILI booklet and collect the information of any medically-attended adverse events which have occurred within 30 days after the onset of the of ILI.

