13.3 Unsolicited Adverse Events

If the reporting source is collected in the study, specify the following: The first-line analysis will use unsolicited adverse event data from all reporting sources combined. A second-line analysis will encompass the analysis of unsolicited adverse events by source (medical records, study specific worksheet).

All the unsolicited adverse events occurring during the study, judged either as probably related, possibly related, or not related to vaccination by the investigator, will be recorded. Safety data including medically-attended AE within 30 days after first occurrence, and RT-PCR confirmed ILI, adverse events leading to withdrawal, AESI, NOCD and SAE up to Day 366 will be captured. The original verbatim terms used by investigators to identify adverse events in the CRFs will be mapped to preferred terms using the MedDRA dictionary. The unsolicited adverse events will then be grouped by MedDRA preferred terms into frequency tables according to system organ class. Adverse events judged by the investigator as at least possibly related to study vaccine will be

summarized by vaccine group, according to system organ class and preferred term within system organ class. When an unsolicited adverse event occurs more than once for a subject, the maximal severity and strongest relationship to the vaccine group will be counted.

Only vaccine-emergent adverse events (see [section 8.7](#) for definition) will be analyzed, i.e., excluding those after a subject has given informed consent but before vaccination. The selection of unsolicited adverse events and the assignment to time intervals will be done by day of onset and not by days ongoing/persisting.

The summaries will be presented by period of onset and will include frequency distributions of the different adverse events:

- Onset between Day 1 and Day 22.
- Onset between Day 23 and Day 181.
- Onset between Day 182 and Day 366
- Onset between Day 1 and Day 366

A number of adverse events typically captured on diary cards will be reported as unsolicited adverse events. Unsolicited adverse events corresponding to local and systemic solicited events (for example, injection site pain, fatigue, etc.), which occur in the 7 days following vaccination, will be presented by treatment group.

The analysis of unsolicited adverse events comprises the following categories:

- Any unsolicited adverse event.
- Possibly or probably related unsolicited adverse events.

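### The question about physician's-office visits is asked at Days 22 and 181 but not at the other safety contacts, so one recall cue is not uniform across the reported intervals

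*Protocol*

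**What the plan says.** Two sections set the scheduled safety contacts before the last visit. Protocol 5.3.1: "Safety follow-up clinic visits will be performed on Days 22 and 181". Protocol 5.3.2: "Safety follow-up calls will be performed on Days 15, 91 and 271". The termination visit is Day 366 (5.5), and an early termination visit repeats its procedures where possible (5.5.1).

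The health-care-contact question differs between them:

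- Days 22 and 181 (5.3.1): hospitalised, or "evaluated at an emergency room or a physician's office for any illness since the site's last contact".
- Days 15, 91 and 271 (5.3.2): "hospitalized or was evaluated at an emergency room for any illness since the site's last contact with the subject".
- Day 366 (5.5): "Ask the subject as to whether he or she was hospitalized or was evaluated at an emergency room for any illness".

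NOCD and AESI are part of the primary safety objectives and are collected for 365 days (Protocol 2.1). Protocol 8.4.2.1.3 and SAP 8.2.1 divide unsolicited events into Day 1-22, Day 23-181, Day 182-366 and the whole year. SAP 13.3 presents summaries by period of onset, including "Onset between Day 182 and Day 366", and lists NOCD and AESI among the analysed categories.

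**The concern.** Many new chronic diagnoses, and non-serious AESIs, may be made in a physician's office without a hospital or emergency room attendance. A question limited to hospital and emergency room does not cue the subject to recall them. If the broader question is asked in one reporting interval and not in the next, ascertainment is not the same in columns printed side by side.

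The difference does not look deliberate. Day 366 is a clinic visit like Days 22 and 181, so clinic versus telephone does not explain it, and no reason is given. The narrower question is also out of step with the protocol's own definition of a medically attended event, which includes a visit to or by a health care provider (Definitions; 7.1.2).

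At stake are how far the interval rates can be compared and, to a lesser degree, the completeness of the one-year NOCD and AESI percentages. The efficacy conclusion is not touched.

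**Working it through.** The plan states no figure on this point, so the check sets the contacts side by side and counts days.

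**Inputs.** Contact days and question wording come from Protocol 5.3.1, 5.3.2 and 5.5; intervals from SAP 13.3. Look-back is taken as the days since the previous scheduled safety contact, starting at Day 1.

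| Day | Contact | Look-back (days) | Office question |
|---|---|---|---|
| 15 | call | 15 - 1 = 14 | no |
| 22 | clinic | 22 - 15 = 7 | yes |
| 91 | call | 91 - 22 = 69 | no |
| 181 | clinic | 181 - 91 = 90 | yes |
| 271 | call | 271 - 181 = 90 | no |
| 366 | clinic | 366 - 271 = 95 | no |

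**By reporting interval.**

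| Interval | Contacts | Hospital/ER question | NOCD/AESI assessed | Office question | Days the office question covers |
|---|---|---|---|---|---|
| Day 1-22 | 2 | 2 | 2 | 1 | 7/21 = 33% |
| Day 23-181 | 2 | 2 | 2 | 1 | 90/159 = 57% |
| Day 182-366 | 2 | 2 | 2 | 0 | 0/185 = 0% |
| Year | 6 | 6 | 6 | 2 | 97/365 = 27% |

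These are shares of calendar days under one prompt, not shares of events found.

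**Ambiguity in the look-back.** The question refers back to the site's last contact. Subjects also receive weekly influenza-like-illness calls or messages to Day 181 or season end (5.3.3). If one of those counts as the last contact, the Day 181 question covers about 7 of 159 days, or 4%.

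**Scale for overall detection.** Protocol 8.5 gives 99% probability of detecting an event of rate 0.001 with 4,860 subjects per group. That reproduces: 1 - (1 - 0.001)^4860 = 99.2%. If a fraction s of all events were ascertained, the probability would be 1 - (1 - 0.001s)^4860:

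- s = 0.90: 98.7%
- s = 0.75: 97.4%
- s = 0.50: 91.2%

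The values of s are assumptions, applied to all events over the whole year. The real loss would be confined to events that this one cue alone would have brought out.

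**The case against.** The strongest reply is that the events themselves are still asked about.

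- NOCDs and AESIs are named in the interview at Days 91, 181, 271 and 366 (5.3.1, 5.3.2, 5.5), and the follow-up Time and Events table marks the assessment at all four.
- Section 7.1.4.1 requires a question on any new diagnosis at each visit. Section 5 counts calls as visits, so it applies twice after Day 181. Since NOCD is defined as a new diagnosis of a chronic condition (7.1.3), that question reaches the endpoint more directly than one about where care was received.
- Subjects are reminded at Days 22 and 181 and at every call, including Day 271, to contact the site about a condition leading to a doctor's visit; 7.1.2 gives a similar instruction for medically attended events.
- Calls follow a script that is not in the documents, so the operative wording may be broader than the protocol sentence.
- There is no safety success criterion (8.2.1.1), and SAP 13.3 specifies no trend test across intervals.

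All of this stands, and it reduces the point to one cue. It does not remove it: the same interview and new-diagnosis question also apply at Day 181, where the office question is asked in addition. The reminder is prospective and depends on self-report. Influenza-like-illness visits and 30-day calls do pick up provider visits, but only in subjects with such an illness.

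A reader might infer that late NOCD and AESI go unprobed, that their rates must fall after Day 181 by design, or that the one-year percentages are certainly understated. The documents support none of these. Nor is the gap confined to the period after Day 181: under the scheduled-contact look-back, Days 1-15 and 22-91 also lack the question, and under the weekly-contact reading the contrast between the last two intervals shrinks to 4% against 0%.

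**Conclusion.** The inconsistency is real and minor. One supplementary prompt is present at two of six scheduled safety contacts and at none in Day 182-366. It may modestly lower capture of non-serious, office-diagnosed NOCD and AESI in the periods without it, so the interval tables may not be fully comparable and the one-year rates may be slightly incomplete. The size in events cannot be derived, because the documents say nothing about how many would be missed by the named query, the new-diagnosis question and self-report yet found by the office question.

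This rests on two assumptions: that the scripts follow the protocol sentences, and that look-back runs from the previous scheduled safety contact. Both arms are asked identically in an observer-blind trial, so nothing here suggests a distorted comparison between vaccines.

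**What to change.** In Protocol 5.3.2 and 5.5 (which carries over to 5.5.1), and in the call and visit scripts, use the 5.3.1 question at every safety contact: hospitalised, or evaluated at an emergency room or a physician's office. In all three sections, define the look-back as since the last scheduled safety contact, so that a weekly surveillance message does not shorten it.

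For subjects already past these contacts, footnote the NOCD and AESI interval tables to say that the prompt differed between contacts, so that a difference between intervals is not read as a time trend.

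The cost is a few words in the protocol and scripts and slightly more non-serious events to record. No contacts are added. If the change comes part-way through a multi-season trial, earlier and later subjects will have had different prompts; the same footnote can say so.
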